### 13.1. Disease Response Criteria

Evaluation of response and disease progression will be made by the Investigator according to RECIST v1.1 ([Eisenhauer et al., 2009](#)) guidelines except for mCRPC which will follow the PCWG3 modified RECIST v1.1 guidelines ([Scher et al., 2016](#)).

#### 13.1.1. Evaluation of Target Lesions

For target lesions, classifications of disease response include Complete Response (CR), Partial Response (PR), Stable Disease (SD), and Progressive Disease (PD).

- **CR:** Disappearance of all target lesions. Any pathological lymph nodes (whether target or non-target) must have reduction in short axis to  $<10$  mm. In the case of mCRPC, PSA levels must also decline to  $<0.2$  ng/ml (undetectable).
- **PR:** At least a 30% decrease in the sum of the diameters of target lesions, taking as reference the baseline sum of longest lesion diameters. In the case of mCRPC, PSA levels must also decline by  $\geq 50\%$  from baseline and the absolute decrease must be at least 2 ng/ml from baseline.
- **SD:** Neither sufficient decrease to qualify for PR nor sufficient increase to qualify for PD, taking as reference the smallest sum of longest diameters while on study, and in the case of mCRPC, the PSA level.

- **PD:** At least a 20% increase in the sum of longest diameters, taking as reference the smallest sum on study (this includes the baseline sum if that is the smallest on study). In addition to the relative increase of 20%, the absolute increment in the sum of longest diameters must be at least 5 mm. In the case of mCRPC, an increase in PSA  $\geq 25\%$  above the nadir with an absolute concentration  $\geq 2$  ng/ml at 2 time points at least 3 weeks apart constitutes PSA progression.

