### **13.2.7. Percentage Change from Baseline in Sum of Diameters of Target Lesions**

Best percentage change from baseline in the sum of longest diameters of target lesions will be summarized descriptively by dose level among subjects enrolled to Part 1 and tumor cohort for Part 2A and 2B subjects. Best percentage change from baseline in sum of longest diameters will

be presented in a Waterfall Plot with corresponding dose level, best overall response, and primary cancer diagnosis identified. Individual percentage changes from baseline in sum of diameters of target lesions overtime will be presented in a spider plot with treatment identified. Scatter plot and dose response curve based on E-max model in percentage change from baseline in sum of diameters of target lesions will also be provided.

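### SAP 13.1.1 judges target lymph nodes on the short axis for CR but sums longest diameters for PR, SD and PD, and SAP 13.2.7 uses two different sums, so the percentage-change outputs can disagree with each other and with the response shown beside them

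*SAP*

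**What the plan says.** **SAP 13.1.1, target lesions.** The CR bullet uses the short axis: "Any pathological lymph nodes (whether target or non-target) must have reduction in short axis to" below 10 mm. The PR bullet requires "At least a 30% decrease in the sum of the diameters of target lesions", "taking as reference the baseline sum of longest lesion diameters". The SD bullet is set by "taking as reference the smallest sum of longest diameters while on study", and the PD bullet by "At least a 20% increase in the sum of longest diameters", with an absolute increase of at least 5 mm. None of the last three treats nodes separately.

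**SAP 13.2.7.** The descriptive summary, and with it the waterfall plot, uses "Best percentage change from baseline in the sum of longest diameters of target lesions". The section heading says *sum of diameters*, as does the next display: "Individual percentage changes from baseline in sum of diameters of target lesions overtime will be presented in a spider plot". The sentence on the scatter plot and E-max curve also says *sum of diameters*. The waterfall must identify each subject's best overall response.

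**Who assigns response.** SAP 13.1 gives the assessment to the Investigator under RECIST v1.1 (PCWG3-modified for mCRPC). Protocol 10.5.5 refers the category definitions to RECIST v1.1, and Appendix B of both documents has tumors measured under it. SAP Section 1 says that the SAP's statistical methods supersede the protocol's.

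Neither document states which axis of a target node enters the sum.

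**The concern.** A node has two different axes, and the SAP uses one for CR and names the other for everything else. Followed literally, a subject whose target lesions are nodal can meet the CR condition on one axis while the sum of longest diameters falls by less than the 30% needed for PR. In the other direction, short-axis growth large enough for PD can leave the sum of longest diameters unchanged.

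The outputs most exposed are those of 13.2.7, because they are percentage changes in lesion measurements and not response categories. The waterfall puts best overall response next to the bar, so a CR could stand beside a bar that does not reach -30%. If a programmer takes the two terms in 13.2.7 at face value, the same subject can also have one value in the waterfall and another in the spider plot and E-max fit. Nodal disease is expected: protocol 7.2.10 provides for measuring lesions in subjects with lymph node metastases.

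**Working it through.** The plan states no figure that depends on this point, so there is none to reproduce. The thresholds come from SAP 13.1.1: nodal CR below 10 mm short axis; PR at -30% or lower; PD at +20% or more and at least +5 mm. The documents give no node dimensions, so all sizes below are assumptions (short x long axis). Each case takes the node as the only target lesion and a single follow-up assessment, with the same axis at both visits.

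Formula: percentage change = 100 x (follow-up sum - baseline sum) / baseline sum.

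**Case 1, shrinking node, 16 x 26 to 9 x 20 mm.**
- Nodal CR rule: 9 mm is below 10 mm, so it is met.
- Longest diameter: (20 - 26)/26 = -23.1%, which does not reach the PR threshold.
- Short axis: (9 - 16)/16 = -43.8%.

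**Case 2, growing node, 15 x 30 to 21 x 30 mm.**
- Longest diameter: (30 - 30)/30 = 0%, which is SD.
- Short axis: (21 - 15)/15 = +40%, an increase of 6 mm, which meets both parts of the PD rule.

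**Range for a node in CR.** Take a baseline of 15 x 22 mm and a follow-up short axis of 9 mm. The short-axis change is (9 - 15)/15 = -40%. With a follow-up longest diameter between 9 and 20 mm, the longest-diameter change runs from (9 - 22)/22 = -59.1% to (20 - 22)/22 = -9.1%. The two axes can therefore differ in either direction.

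**When there is no discrepancy.** If both axes shrink in proportion, the percentages are equal: 15 to 9 mm is -40% on either axis. The discrepancy needs a change of node shape.

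**Dilution by other lesions.** Add 20 mm of unchanged non-nodal disease to Case 1. Longest diameter: (40 - 46)/46 = -13.0%. Short axis for the node: (29 - 36)/36 = -19.4%. The gap falls from about 21 to about 6 percentage points.

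**The case against.** The strongest answer is that response is not derived from this text. The Investigator assigns it under RECIST v1.1, SAP Table 4 combines categories and not millimetres, and SAP Section 19 declares no change from the protocol's analyses. A reader might infer that ORR, CBR and PFS are wrong for nodal subjects. The documents do not support that, since those endpoints need not be computed from the 13.1.1 bullets. This objection stands, and it confines the effect on categories to checks programmed from those bullets.

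A reader might also infer that an unchanged node can score as a PR. That needs longest diameter at baseline and short axis at follow-up: for a 16 x 26 mm node, (16 - 26)/26 = -38.5%. The PR bullet does mix its terms, but it never mentions the short axis, and longest diameter at both visits gives 0%. Even on the mixed reading, with an all-nodal sum the short axis must be at most 0.70 of the long axis. At a ratio of 0.6, nodes must make up at least 0.30/(1 - 0.6) = 75% of the baseline sum. This is too strained to count as a consequence of the plan.

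Two smaller points also stand. The E-max sentence already says *sum of diameters*, so that curve is not stated to rest on longest diameters. And because the waterfall identifies best overall response, an Investigator-assessed CR or PR stays visible whatever the bar height.

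What the objection does not remove is the conflict of axes inside 13.1.1 and the use of two terms for one quantity in 13.2.7.

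**Conclusion.** The point holds as a conflict between stated rules, with limited reach. SAP 13.1.1 uses the short axis of target nodes for CR and longest diameters for the PR reference, the SD reference and the PD increase. SAP 13.2.7 is split between two terms. For subjects with nodal target lesions, the waterfall value can disagree with the best overall response shown beside it, and with the same subject's spider and E-max values if the two terms are programmed differently.

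The sizes (-23% against -44%, and 0% against +40%) are illustrations. They rest on assumed node dimensions, a change of node shape, and a sum that is wholly nodal. How often this would occur cannot be estimated, because the documents do not give the share of subjects with nodal targets. No sample size, operating characteristic or go/no-go rule depends on it. It is worth correcting because the affected outputs are the plan's displays of tumor shrinkage by dose and cohort, and the correction is cheap.

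**What to change.** Define one *sum of diameters* in SAP 13.1.1: longest diameter for non-nodal target lesions and short axis for nodal target lesions, on the same axis at baseline, nadir and every follow-up. This extends the axis that the SAP's own CR bullet already uses for nodes. Use the term in the PR, SD and PD bullets and in every 13.2.7 output (best-change summary, waterfall, spider, scatter and E-max), replacing *sum of longest diameters*.

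State also, in the text and as a waterfall footnote, that a nodal CR can leave a non-zero sum. Under the revised definition Case 1 still plots at -44%, not -100%.

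The cost is SAP wording and one derivation. Before the change is made, confirm that the eCRF records the short axis of target nodes at every assessment; the documents do not say whether one or two axes are captured.

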7.2.10. Response Assessments

Assessments of response and progression will occur in accordance with RECIST v1.1 ([Eisenhauer et al., 2009](#)) at timepoints shown in the Schedule of Events ([Appendix A](#) and [Appendix B](#)). Subjects with mCRPC will be assessed per PCWG3 guidelines ([Scher et al., 2016](#)).

All subjects must have contrast-enhanced imaging studies of chest, abdomen, and pelvis as well as other areas of suspected disease within 28 days prior to their first dose of study treatment. The preferred imaging modality is contrast-enhanced computed tomography (CT). In subjects for whom IV contrast for CT is contraindicated, perform contrast-enhanced magnetic resonance imaging (MRI) scanning of the aforementioned anatomic regions with non-contrast enhanced CT of the chest. Subjects known to have fluorodeoxyglucose (FDG)-avid tumors are required to undergo positron emission tomography (PET) scanning along with the CT scan at Screening. Subjects whose tumors demonstrate FDG update at Screening should undergo follow-up PET scanning post-Cycle 6, post-Cycle 12, and every 6 cycles thereafter (see below). Subjects with skin, subcutaneous or lymph node metastases may also have evaluations of measurable lesions (including measurements, with a ruler or calipers) by means of physical examination.

Subjects with mCRPC must have a baseline PSA and bone scan in addition to the aforementioned imaging studies. (Note: A rising PSA as the sole indicator of disease activity will not lead to a determination of disease progression.) On-treatment bone scans will be performed at the same time points as CT/MRI scans. As a rule, the same imaging modality (ie, CT or MRI or combined CT/PET scans) should be used for all scheduled tumor assessments and measurements.

Imaging studies should be repeated prior to Cycle 3 (ie, end of Cycle 2) and every 2 cycles thereafter (ie, end of Cycles 4, 6, 8, etc). There is a 7-day window for imaging procedures to allow time for availability of results prior to the next cycle. If an imaging procedure must be scheduled to occur outside the 7-day window, this should be discussed with the Medical Monitor for approval prior to the procedure.

Response assessments, including imaging studies, are to be performed at the EOT visit, if PD has not already been established and the last response assessment was conducted >4 weeks prior to EOT.

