## **7. GENERAL STATISTICAL CONSIDERATIONS**

### **7.1. Unit of Analysis**

There are several units of analysis in this study. For select efficacy summaries based on the RECIST v1.1 criteria, specifically in the melanoma, mesothelioma, mCRC, and all-tumors cohorts in Part 2A and 2B (Tumor-Specific Dose Expansion and Dose Optimization), the unit of analysis will be the tumor, however, the overall response will be evaluated at the subject level. The tumor is defined as any target, non-target, or new lesions, including metastases, identified

during screening and follow-up imaging. In the case of mCRPC, the study unit will be the subject for efficacy summaries based on the PCWG3 modification of RECIST v1.1 which includes PSA and bone lesion assessments. Slit lamp and visual acuity summaries will be at the eye level. Additionally, AEs, SAEs, clinical laboratory data, physical examination findings, ECG, ECOG PS, biomarker data, and medical history will be presented at the subject level.

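### SAP 13.1.1 lists a confirmed PSA rise under progressive disease for mCRPC, against protocol 7.2.10, and adds undeclared PSA conditions to CR and PR

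*SAP*

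**What the plan says.** **Protocol.** Section 7.2.10 says of mCRPC: "A rising PSA as the sole indicator of disease activity will not lead to a determination of disease progression". Sections 2.2.2.1 and 10.5.5 refer mCRPC response and clinical benefit to the PCWG3 guideline and give no PSA threshold. Section 4.2.2 excludes men whose only progression is biochemical, and sets no minimum PSA for entry.

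**SAP 13.1.1** writes PSA into all four target-lesion categories for mCRPC:
- **CR:** "In the case of mCRPC, PSA levels must also decline to" below 0.2 ng/ml.
- **PR:** "In the case of mCRPC, PSA levels must also decline by" at least 50% "from baseline and the absolute decrease must be at least 2 ng/ml from baseline".
- **SD:** judged by "taking as reference the smallest sum of longest diameters while on study, and in the case of mCRPC, the PSA level".
- **PD:** a PSA at least 25% above nadir, at 2 ng/ml or more, "at 2 time points at least 3 weeks apart constitutes PSA progression".

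**Elsewhere in the SAP.** Section 7.1 bases the mCRPC efficacy summaries on a "PCWG3 modification of RECIST v1.1 which includes PSA and bone lesion assessments". Section 13.1.2 makes non-target CR depend on the tumor marker becoming normal, and Appendix C gives a PSA reference range of under 4 ng/mL. Section 1 says the SAP's statistical methods override the protocol's. Section 19 reports no changes from the protocol.

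**The concern.** A subject with stable scans and a confirmed PSA rise is not a progressor under the protocol, but on the natural reading of SAP 13.1.1 is scored PD. Three endpoints depend on that call. PFS and DOR end at PD or death (SAP 13.2.2 and 13.2.3). CBR needs CR, PR or SD over at least two assessments (SAP 13.2.5). CBR also drives the Part 2A decision at 15 subjects (protocol 10.6, SAP 5), so an active mCRPC cohort could be closed by a rule that the protocol excludes.

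The PSA conditions on CR and PR are a second and different matter. They change what counts as an objective response without being listed as a change.

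**Working it through.** **1. Does a PSA rise lead to PD?** The PSA sentence stands inside the PD bullet. The SD bullet requires that there be no increase sufficient for PD and names the PSA level as a reference for mCRPC; that clause does nothing unless a PSA rise can count toward PD. SAP Table 4 then makes overall response PD whenever the target-lesion column is PD, whatever the other columns show, so no separate PSA row is needed. The sentence does, however, end at PSA progression and never says PD outright.

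**2. Can the rule be triggered in practice?** Appendices A and B schedule PSA for mCRPC at baseline and around the end of each 28-day cycle, so readings at least 3 weeks apart will normally exist. Scans fall at the ends of Cycles 2 and 4, so a rise confirmed before the second scan can remove clinical benefit.

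**3. The plan's own figure.** Under the rule in protocol 10.6 and SAP 5, a cohort stops if at most 1 of 15 subjects has clinical benefit:

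Pr(futility) = (1 − p)^15 + 15p(1 − p)^14

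At p = 0.20: 0.0352 + 0.1319 = 0.167, which is the stated 17%. The other rows of protocol Table 13 also reproduce: 82.9, 54.9, 31.9, 8.0, 3.5 and 1.4% for true CBR 5, 10, 15, 25, 30 and 35%.

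**4. Effect of reclassification.** Let f be the share of subjects with true benefit who lose that status because of PSA. The documents give no value, so f is an assumption shown over a range. The counted CBR is p(1 − f).

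| f | Counted CBR (true 20%) | Pr(futility) |
|---|---|---|
| 0 | 20% | 16.7% |
| 10% | 18% | 21.9% |
| 20% | 16% | 28.2% |
| 25% | 15% | 31.9% |
| 40% | 12% | 44.8% |
| 50% | 10% | 54.9% |
| 60% | 8% | 66.0% |

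At a true CBR of 30%, f = 10, 25 and 50% gives 5.8, 11.7 and 31.9%, against 3.5% at f = 0.

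**5. The PR condition.** PSA cannot fall by more than its baseline value B. A fall of at least 2 ng/ml is therefore impossible when B < 2, whatever the scans show, and entry sets no minimum PSA. For B between 2 and 4 ng/ml the absolute condition is the stricter of the two, since half of B is then less than 2.

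**6. The CR condition.** A PSA of, say, 1 ng/ml lies inside the Appendix C range, the only PSA reference range in the SAP, and so would count as normal for non-target CR. It fails the 0.2 ng/ml limit for target-lesion CR. The two sections therefore apply different PSA limits to the same subject.

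**The case against.** The strongest reply is that the SAP never equates PSA progression with PD. The inputs to Table 4 are lesions, SAP 13.1 leaves evaluation to the Investigator, and protocol 7.2.10 tells sites that PSA alone is not progression. If the analysis simply takes Investigator categories, the protocol rule may still operate. SAP 1 also claims precedence only for statistical methods. This stands to the extent that the error in PFS and CBR is possible rather than certain. It does not remove the conflict: SAP 13.1.1 sets out the criteria and does not say which rule prevails, so two programmers could derive different PFS and CBR from the same data.

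A reader might infer that ORR is also shown to be wrong. The documents do not support that. Protocol 7.2.10 concerns progression only and does not forbid a PSA condition for response. Whether the cited prostate cancer guideline keeps PSA apart from lesion response cannot be checked here. What can be said is that the conditions are added, undeclared and internally inconsistent.

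A reader might also take the 28, 45 and 66% as expected effects. They are not, for two reasons. A rise confirmed after two qualifying assessments does not undo clinical benefit already met. A lesion PR downgraded to SD only for lack of a PSA fall still counts toward CBR if held over two assessments. So f will be smaller than the share of subjects who ever have a confirmed PSA rise.

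**Conclusion.** The conflict between SAP 13.1.1 and protocol 7.2.10 is real and undeclared. On the natural reading, a PSA-only rise is PD, which could advance PFS events, shorten DOR and lower CBR in the mCRPC cohort. At a true CBR of 20%, the chance of stopping for futility would rise from the stated 17% to 28, 45 or 66% if 20, 40 or 60% of subjects with true benefit lost that status. Those shares are assumed and the figures are upper-end illustrations.

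For ORR the finding is narrower: undeclared PSA conditions, one of which cannot be met below a baseline PSA of 2 ng/ml, and a CR limit of 0.2 ng/ml that does not match the marker-normalization rule with its 4 ng/mL range.

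This is a should-fix. It affects the secondary endpoints and the futility decision of one cohort among up to four tumor types; the primary endpoints of Parts 2A and 2B are safety and identification of the recommended Phase 2 dose.

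**What to change.** Before any mCRPC data are scored for the interim analysis:

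1. Remove PSA from the PD and SD bullets of SAP 13.1.1, and state that PSA progression alone is not a PD event for PFS, DOR or CBR, in line with protocol 7.2.10.
2. Report PSA response and PSA progression as separate summaries.
3. For CR and PR, either remove the PSA conditions, or declare them in SAP 19 and report imaging-only ORR alongside. If they stay, say how a subject with baseline PSA below 2 ng/ml is to be classified.
4. Reconcile the PSA limit for CR across SAP 13.1.1, SAP 13.1.2 and Appendix C.
5. Align SAP 7.1, so that it does not describe PSA as an input to categories from which it has been removed.

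The cost is SAP wording, one PSA table and, if the composite is kept, one further ORR summary. PSA and scans are already scheduled, so no new data are needed.

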### 13.1.2. Evaluation of Non-Target Lesions

For non-target lesions or subjects with non-measurable disease, classifications of disease response include CR, non-CR/non-PD, and PD.

- **CR:** Disappearance of all non-target lesions and normalization of tumor marker level. All lymph nodes must be non-pathological in size (<10 mm short axis).
- **Non-CR/Non-PD:** Persistence of 1 or more non-target lesion(s) and/or maintenance of tumor marker level above the normal limits.
- **PD:** Unequivocal progression of existing non-target lesions, or appearance of 1 or more new lesions. When the subject also has measurable disease, to achieve ‘unequivocal progression’ on the basis of non-target disease, there must be substantial worsening in nontarget disease such that, even in the presence of SD or PR in target lesions, the overall tumor burden has increased sufficiently to merit discontinuation of therapy.

## 13.2. Criteria for Overall Response

Listings of the various disease response parameters collected for each subject will be provided. Disease response categories include: Complete Response (CR), Partial Response (PR), Stable Disease (SD), Progressive Disease (PD), and Not Evaluable (NE). If a subject misses a disease assessment, or the Investigator is unable to assign a response category at a particular response assessment timepoint, response for this timepoint will be designated NE. Additionally, if a subject leaves the study prior to any disease assessment and is lost to follow-up, best overall response will be assigned as NE. The overall response is categorized based on the criteria in [Table 4](#).

**Table 4: RECIST 1.1 Criteria for Categorizing Target Disease Overall Response**

Target Lesions	Non-Target Lesions	New Lesions	Overall Response
CR	CR	No	CR
CR	Non-CR/Non-PD	No	PR
CR	Not evaluated	No	PR
PR	Non-PD or not all evaluated	No	PR
SD	Non-PD or not all evaluated	No	SD
Not all evaluated	Non-PD	No	NE
PD	Any	Yes or No	PD
Any	PD	Yes or No	PD
Any	Any	Yes	PD

At the conclusion of study drug treatment, the best overall response will be determined. Best overall response is defined as the best response recorded from the start of the study treatment until the end of treatment.

### 13.2.1. Objective Response Rate (ORR)

Objective response is defined as a best overall response of CR or PR. The proportion of subjects with a best response of CR or PR following KZR-261 treatment will be summarized using frequencies and percentages. Only confirmed responses will be included in the calculation of ORR. Additionally, the response rates for individual categories of CR, PR, SD, PD, or NE will be summarized by frequency distributions. Two-sided 90% CIs using the Clopper-Pearson approach for ORR will be calculated using SAS® code as:

```
proc freq;
tables response / binomial (level='Yes' cl=EXACT);
exact binomial;
run;
```

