10.5.8. Handling of Missing Data

Subjects discontinue study treatment and/or the study for any reason will be included in all analyses regardless of the duration of treatment. There will be no imputation for missing data, unless otherwise specified in the Statistical Analysis Plan.

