### **7.4. Data Analysis Conventions**

All data analysis will be performed by [REDACTED] after the study is completed and the database has been locked. Statistical programming and analyses will be performed using SAS® version 9.4 or higher. Output will be provided in rich text format (RTF) for tables and portable document format (PDF) for tables, listings, and figures using landscape orientation. All study data will be listed by subject, dose level in Part 1 (Dose Escalation) and cohort in Part 2A and 2B (Tumor-Specific Dose Expansion and Dose Optimization), and visit (as applicable) based on all enrolled subjects unless otherwise specified. Listings will be sorted by dose level in Part 1 (Dose Escalation) and by cohort in Part 2A (Tumor-Specific Dose Expansion) and Part 2B (Dose Optimization), subject number, visit/time point, and parameter as applicable.

Summaries for continuous and ordinal variables will include the number of observations (n), arithmetic mean, standard deviation, median, minimum, and maximum. Minima and maxima will be reported with the same precision as the raw values; means and medians will be presented to one additional decimal place than reported in the raw values. Standard deviations will be presented to two additional decimal places than reported in the raw values. Summaries for discrete variables will include counts and percentages. All percentages will be rounded to one decimal place (ie, XX.X%). Changes from baseline will be calculated as follow-up visit minus baseline.

Unless otherwise specified, all data will be summarized by dose level and overall, for Part 1 (Dose Escalation), tumor-specific cohort for Part 2A (Dose Expansion), and dose and tumor-specific cohort for Part 2B (Dose Optimization).

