### **13.2.3. Progression-Free Survival (PFS)**

PFS is defined as the date of initiation of KZR-261 until the date of documented PD or death from any cause, whichever occurs first.

$$PFS \text{ (weeks)} = \frac{([Date \text{ of } PD \text{ or } Death - Date \text{ of } First \text{ Dose} \text{ of } KZR - 261] + 1)}{7}$$

For subjects who have neither progressed nor died, PFS will be censored at the date of the last evaluable disease assessment. The median PFS will be estimated using Kaplan-Meier methods and summarized.

Progression-Free Survival at 4 months (PFS4) is defined as the percentage of subjects alive and progression-free at 4 months (ie, 17 weeks) after the initiation of study treatment. The PFS4 responders will be summarized using frequencies and percentages. Similar to analysis of ORR, two-sided 90% CIs for PFS4 responders using the Clopper-Pearson approach will be calculated.

Progression-Free Survival at 6 months (PFS6) is defined as the percentage of subjects alive and progression-free at 6 months (ie, 26 weeks) after the initiation of study treatment. The PFS6 responders will be summarized using frequencies and percentages. Similar to analysis of ORR, two-sided 90% CIs for PFS6 responders using the Clopper-Pearson approach will be calculated.

Separate Kaplan-Meier plots for subjects enrolled to Parts 1, 2A, and 2B will be provided.

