### **13.2.5. Clinical Benefit Rate (CBR)**

Clinical benefit is defined as achieving a best response of CR, PR, or SD over 2 or more response assessment timepoints. Subjects meeting the criteria for clinical benefit will be summarized using frequencies and percentages. Like analysis of ORR, two-sided 90% CI using the Clopper-Pearson approach will be calculated.

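### SAP 13.2.1 promises 90% exact confidence intervals, but its printed PROC FREQ step sets no level and at the SAS default returns 95% limits (minor)

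*SAP*

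**What the plan says.** SAP 13.2.1 commits to "Two-sided 90% CIs using the Clopper-Pearson approach for ORR" and gives the code that will calculate them. The TABLES statement reads "tables response / binomial (level='Yes' cl=EXACT", then a closing bracket and semicolon. An EXACT statement follows. Neither carries a confidence-level option. SAP 7.4 names the software: "Statistical programming and analyses will be performed using SAS".

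The same method and level are carried to three other endpoints. For PFS4, SAP 13.2.3 says "Similar to analysis of ORR, two-sided 90% CIs for PFS4 responders using the Clopper-Pearson approach will be calculated", with parallel wording for PFS6. For CBR, SAP 13.2.5 says "two-sided 90% CI using the Clopper-Pearson approach will be calculated". The 90% level is thus stated four times. Protocol 10.5.5 names the exact two-sided method but gives no level.

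On the landmarks, SAP 13.2.3 sets PFS4 at 17 weeks and PFS6 at 26 weeks and reports both as simple proportions; for PFS6, "The PFS6 responders will be summarized using frequencies and percentages". For subjects with neither event, "PFS will be censored at the date of the last evaluable disease assessment". Protocol 10.5.8 says that subjects who discontinue "will be included in all analyses regardless of the duration of treatment" and that missing data are not imputed unless the SAP says otherwise. SAP 7.2 imputes only dates.

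**The concern.** The text and the code that implements it disagree. A programmer who runs the step as printed would produce intervals labelled 90% that are 95%. Because PFS4, PFS6 and CBR are analysed in the same way as ORR, reusing the step would carry the mismatch to them.

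The secondary question is what happens to a subject whose last scan falls shortly before a landmark. SAP 13.2.3 does not say whether that subject counts as progression-free, counts as not progression-free, or leaves the denominator. One dataset can then give more than one PFS4 or PFS6.

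**Working it through.** **Confidence level**

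The SAP prints no interval, so the figure to reproduce is the stated level, alpha = 0.10. The printed step has no ALPHA=. Assuming the SAS default of 0.05, the code gives alpha = 0.05, and the stated level is not reproduced. SAS itself was not run.

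With x responders among n and level 1 − α, the Clopper-Pearson limits are:

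- lower = Beta quantile at α/2 with parameters (x, n − x + 1), or 0 if x = 0
- upper = Beta quantile at 1 − α/2 with parameters (x + 1, n − x)

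For x = 0 the upper limit is 1 − (α/2)^(1/n). For n = 15 this is 1 − 0.05^(1/15) = 18.1% at 90% and 1 − 0.025^(1/15) = 21.8% at 95%.

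The sizes 15 and 35 are the interim and maximum Part 2A cohort sizes (Protocol 10.6). The counts are illustrative.

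| x/n | 90% (text) | 95% (code) | width ratio |
|---|---|---|---|
| 0/15 | 0-18.1% | 0-21.8% | 1.20 |
| 2/15 | 2.4-36.3% | 1.7-40.5% | 1.14 |
| 3/15 | 5.7-44.0% | 4.3-48.1% | 1.14 |
| 0/35 | 0-8.2% | 0-10.0% | 1.22 |
| 7/35 | 9.8-34.3% | 8.4-36.9% | 1.16 |
| 9/35 | 14.1-40.6% | 12.5-43.3% | 1.16 |

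**Scan timing against the landmarks**

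Cycles last 28 days and scans fall at the end of every second cycle (Protocol 7.2.10).

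- PFS4: the end-of-Cycle-4 scan is day 4 × 28 = 112 (week 16). The landmark is day 17 × 7 = 119. A scan 7 days late just reaches it.
- PFS6: the end-of-Cycle-6 scan is day 6 × 28 = 168 (week 24). The landmark is day 26 × 7 = 182. With no cycle delay, a scan 7 days late is on day 175 (week 25), still before it.

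A subject who stops at Cycle 6 without progression has just been scanned. Protocol 8.3.1 then requires no end-of-treatment scan, because one is due only if the last was more than 4 weeks earlier. Later contact is by telephone about every 90 days from the last dose. Cycle 6 Day 15 is study day 5 × 28 + 15 = 155, so the first call is near day 245, after the landmark. It can report progression, but the SAP does not say whether such a report is used.

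**Why the counting rule matters (assumed counts, n = 35)**

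Suppose 25 subjects have progressed or died by week 24 and 10 are progression-free at the week-24 scan. Four of these have no later assessment; the other six have later scans and no event dated by week 26. PFS6 is then:

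- unknown counted as not progression-free: 6/35 = 17.1%
- unknown excluded: 6/31 = 19.4%
- unknown counted as progression-free: 10/35 = 28.6%

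Kaplan-Meier at week 26 is also 10/35 = 28.6%.

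**Crude rate or Kaplan-Meier: a simulation on assumed inputs**

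Inputs: n = 35, exponential PFS with median 12 weeks, dropout median 40-80 weeks, scans every 8 weeks, progression dated at the next scan, censoring at the last scan, subjects without a post-baseline scan excluded. A share of subjects has no scan after week 24. Crude means unknown counted as failure. Informative means that subjects progress three times as fast after dropout.

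| Setting | truth | crude | Kaplan-Meier |
|---|---|---|---|
| PFS4, non-informative | 37.5% | 30-35% | 40% |
| PFS6, non-informative, 0% stop scanning | 22.3% | 16.7-20.5% | 25% |
| PFS6, non-informative, 25% stop | 22.3% | 12.6-15.3% | 25% |
| PFS6, non-informative, 50% stop | 22.3% | 8.4-10.2% | 25% |
| PFS4, informative | 32-35% | 30-35% | 39-40% |
| PFS6, informative, 25% stop | 16-19% | 12.5-15% | about 25% |

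Kaplan-Meier is better for PFS6 when censoring is non-informative and 25-50% stop scanning. The crude rate is nearer for PFS4 in every informative setting, and for PFS6 with informative dropout and 25% stopping. Kaplan-Meier runs 2-3 points high even when censoring is non-informative, because it in effect reads the rate at weeks 16 and 24.

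**The case against.** On the code, the 90% level is unambiguous in prose and the step is a fragment, with no dataset or cohort variable, that a programmer must adapt and would probably correct. The discrepancy also rests on a software default that the documents do not give. All of this stands and keeps the point minor. It does not remove it: the SAP presents the step as the way the 90% limits will be calculated, and nothing in it asks for 90%.

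On the landmarks, Protocol 3.1 lets subjects deriving benefit continue after Cycle 6. They would next be scanned at about week 32, which settles their week-26 status. The censoring rule is written for PFS time, while PFS4 and PFS6 have their own definitions, and telephone contact asks about progression. Counting unknown status as failure is a defensible conservative choice. Protocol 10.5.8, SAP 7.2 and the requirement to be alive and progression-free all lean that way. This stands too. What remains is that no sentence states the rule.

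A reader might infer that Kaplan-Meier must replace the crude rates. The documents do not support that: which estimator is nearer the truth depends on the censoring, and SAP 13.2.3 plans a Kaplan-Meier median and plots but no landmark interval. A reader might also infer that the true rate is bracketed by the crude and Kaplan-Meier values. It need not be: a subject who progresses in weeks 24-26 and is next scanned at week 32 counts as progression-free in both, so the truth can lie below both. Nor is there a conflict with SAP 19, which declares no changes from the protocol. The protocol synopsis makes landmark PFS optional and names no estimator for it.

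**Conclusion.** The code in SAP 13.2.1 is wrong as written against its own text. If run as printed at the SAS default of 0.05, it gives 95% limits under a 90% label. Over the counts checked, intervals are 14-22% wider and individual non-zero limits move by 0.7 to 4.2 points. The consequence is confined to the width of descriptive secondary intervals: the ORR interval directly, and PFS4, PFS6 and CBR only if the step is reused. Point estimates are unchanged. The Part 2A futility rule counts subjects with clinical benefit among 15, uses no interval, and is unaffected.

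The landmark matter is a missing counting rule, not an error in the estimator. The number of subjects affected cannot be derived from the documents; the counts, stopping rates and simulation inputs above are assumptions. Overall severity is minor.

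**What to change.** In SAP 13.2.1, make the TABLES statement "tables response / binomial (level='Yes' cl=EXACT" followed by `) alpha=0.1;`. Keep the 90% level, and use the same option wherever the step is reused for PFS4, PFS6 and CBR.

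In SAP 13.2.3, add two or three sentences stating how a subject of unknown status at week 17 or 26 is counted, whether telephone-reported progression is used, and that the number censored before each landmark will be reported. Kaplan-Meier estimates at weeks 17 and 26 may be added as supportive. If they are, name the confidence interval method and note that with 8-weekly scans they in effect read weeks 16 and 24 and assume non-informative censoring.

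The cost is one code option and a few lines of text. No new data are needed.
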